10.4.4 OTHER IMPORTANT CLINICAL EFFECTIVENESS OUTCOMES

The statistical analyses for the other effectiveness endpoints will be based on the available data of the AT population. The percent change in unmedicated DIOP from baseline at 12 months will be calculated for each study eye as

$$\% \text{ change} = \frac{(12\text{-month unmedicated DIOP} - \text{Baseline unmedicated DIOP})}{(\text{Baseline unmedicated DIOP})} \times 100\%.$$

The number and percent of subjects achieving $\geq 20\%$ reduction in unmedicated DIOP from baseline at 12 months (i.e., 12-month responder) will be calculated. The exact 95% confidence interval of the 12-month responder rate will be calculated by the binomial distribution for each study group separately. The difference in the 12-month responder between OMNI (transluminal viscoelastic delivery AND trabeculotomy) and [REDACTED] groups and the corresponding 95% confidence interval per normal distribution will be calculated. The same statistics will be provided for the difference in the 12-month responder between OMNI (transluminal viscoelastic delivery) and [REDACTED] groups. The same statistical methods will be used to summarize the subjects with an unmedicated DIOP between 6 and 18 mmHg inclusive at 12 months.

The descriptive statistics for the continuous variables will be used to summarize the change in number of ocular hypotensive medications used from screening to 12 months. The ANOVA with study treatment group (three groups) as the factor will be used to compare the mean difference in the change in number of ocular hypotensive medications used from screening to 12 months. The mean difference between OMNI (transluminal viscoelastic delivery AND trabeculotomy) and [REDACTED] and that between OMNI (transluminal viscoelastic delivery) and [REDACTED] will be evaluated using Dunnett's test. The same methods will be used to analyze the percent change in unmedicated DIOP from baseline to 12 months.

The analyses described in this section are exploratory in nature.

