6 STUDY ENDPOINTS

6.1 EFFECTIVENESS ENDPOINTS

The **Primary effectiveness endpoint** is:

- Mean change in unmedicated DIOP from baseline at 12-month postoperative examination

Other effectiveness endpoints are:

- Proportion of eyes with a $\geq 20\%$ decrease in **unmedicated** mean diurnal IOP (DIOP) from baseline
- Proportion of eyes with **unmedicated** mean DIOP between 6 and 18 mmHg inclusive
 - Mean change in the number of ocular hypotensive medications compared to Screening
 - Percent change in **unmedicated** DIOP from baseline

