Another potential reason for intervention is hypotony. Intervention should only be considered if the hypotony has caused or is likely to cause sequelae such as a flat chamber or retinal detachment. No intervention is indicated when the vision is unchanged from screening, there is no persistent choroidal detachment, the anterior chamber is not flat with lens corneal touch, or the patient is asymptomatic. No intervention should be undertaken for hypotony which is not causing, or threatening to cause, a reduction in vision.

Secondary IOP-Lowering Interventions to Control IOP

If the subject requires another glaucoma procedure to control their IOP, the subject should continue to be followed according to standard of care until the adverse event resolves or 1-month post-re-intervention, whichever is longer. Following this, the subject should be withdrawn from the study.

Subjects who have had a secondary IOP-lowering intervention will be considered treatment failures for the purpose of the endpoint analyses. For the primary effectiveness endpoint of the study, the corresponding baseline unmedicated DIOP will be used to impute the 12-month unmedicated DIOP. These subjects will be included in the Safety Endpoint analyses through their withdrawal from the study.

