10.4.1 PRIMARY EFFECTIVENESS ENDPOINT

The primary analysis of the primary effectiveness endpoint will be based on the AT population. The Baseline unmedicated DIOP will be used to impute the 12-month unmedicated DIOP for the subjects meeting any of the following criteria:

- Ocular hypotensive medications cannot be washed out properly at 12 months due to safety reasons.
- Have secondary surgical interventions (such as laser procedure or MIGS) to control IOP before the 12-month washout.
- Have any ocular procedures that can affect the IOP before the 12-month washout.

- Have IOP below 6 mmHg at 1 month or later
- Do not have the 12-month washed out DIOP due to any other reasons.

The change in unmedicated DIOP from baseline at 12 months will be calculated for each study eye as change = (12-month unmedicated DIOP – Baseline unmedicated DIOP).

The descriptive statistics (such as mean, standard deviation, median, minimum, and maximum) of the medication-free mean diurnal IOP and the change from baseline and the 95% confidence interval of the mean will be calculated for each of the three study groups. A two-sample t-test with a one-sided significance level of 0.025 will be used to compare the mean unmedicated DIOP change from baseline at 12 months for Hypotheses I and II described in Section [10.1](#). The two-sided 95% confidence interval based on the t-distribution will also be provided for the mean difference. In order to assess the pattern of the distribution, box-plots will be prepared for the medication-free mean diurnal IOP and its change from baseline for each of the three study groups.

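### Section 10.4.4 gives the two 12-month responder endpoints no failure rule, so eyes that section 8.10 calls treatment failures can leave the denominator or even count as responders

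*Combined protocol and SAP*

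**What the plan says.** Section 6.1 lists the two responder proportions among the other effectiveness endpoints. Section 10.4.4 sets the data rule for them: "The statistical analyses for the other effectiveness endpoints will be based on the available data of the AT population". It describes the 20% responder analysis and then adds: "The same statistical methods will be used to summarize the subjects with an unmedicated DIOP between 6 and 18 mmHg inclusive at 12 months". Each arm gets an exact confidence interval, and each OMNI arm gets a difference from the comparator with a 95% interval. The section states no denominator, no imputation and no rule for failures, and it labels its analyses exploratory.

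Section 8.10 deals with eyes that need a further glaucoma procedure. They are followed until the event has resolved or for one month after the procedure, taking the later of the two. "Following this, the subject should be withdrawn from the study". The section then says: "Subjects who have had a secondary IOP-lowering intervention will be considered treatment failures for the purpose of the endpoint analyses". The next sentence gives the mechanism for one endpoint: "For the primary effectiveness endpoint of the study, the corresponding baseline unmedicated DIOP will be used to impute the 12-month unmedicated DIOP".

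Section 10.4.1 applies the same baseline imputation in the primary analysis to several groups. They include eyes with a secondary procedure to control IOP before the 12-month washout, and eyes meeting this criterion: "Ocular hypotensive medications cannot be washed out properly at 12 months due to safety reasons". Section 10.4.3 says expressly that the covariate analysis uses the primary imputation. Section 10.4.4 does not.

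**The concern.** Both responder endpoints need an unmedicated DIOP at month 12. Three kinds of eye cause difficulty.

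- **Secondary procedure, withdrawn before month 12.** No 12-month value exists. Under an available-data rule the eye leaves numerator and denominator, although 8.10 calls it a failure.
- **Secondary procedure shortly before month 12.** Follow-up may still be running, so a DIOP may be observed. Nothing in 10.4.4 stops that eye from counting as a responder on a pressure produced by the second procedure.
- **Washout unsafe at month 12.** No unmedicated value exists and the eye drops out. The primary analysis scores it as no change.

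At stake is what the responder rates mean. As written they are close to rates among eyes that did not fail. If failures are unevenly spread across arms, the reported between-arm difference is affected too. The responder results could then diverge from the primary result because of definitions alone.

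**Working it through.** **The plan's figure.** The synopsis gives 411 completers and about 10% drop-out. Per arm, 411 / 3 = 137; 137 / 0.90 = 152.2, rounded up to 153; 3 × 153 = 459, which matches the plan. The readable text gives no expected responder rate and no expected frequency of secondary procedures or failed washout. All rates below are therefore assumptions.

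**What the primary rule would imply.** The synopsis requires a baseline unmedicated DIOP of 24 to 39 mmHg. An eye whose 12-month value is set to baseline has 0% change and a DIOP of at least 24, so it fails both responder definitions. Scoring such an eye as a non-responder therefore agrees with the primary analysis.

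**Formula.** In one arm let
- n = eyes with an available DIOP and r = responders among them;
- x = failed eyes with no DIOP (earlier secondary procedure, or unsafe washout);
- s = eyes among the r that count as responders on a post-procedure DIOP.

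The literal 10.4.4 rate is r / n. The rate with failures counted is (r − s) / (n + x). As s and x cannot be negative, the second never exceeds the first. With s = 0 and k = x / (n + x), the inflation is (r / n) × k. Each eye counted in s adds a further 1 / (n + x), which is 1 / 153 = 0.65 points in an arm of 153.

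**Size within an arm (assumed: 70% responders among available eyes, s = 0).**

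| k | Failures counted | Inflation |
|---|---|---|
| 2% | 0.70 × 0.98 = 68.6% | 1.4 points |
| 5% | 0.70 × 0.95 = 66.5% | 3.5 points |
| 10% | 0.70 × 0.90 = 63.0% | 7.0 points |
| 15% | 0.70 × 0.85 = 59.5% | 10.5 points |

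Over assumed rates of 50% to 80% and k of 2% to 15%, the inflation runs from 0.50 × 0.02 = 1.0 to 0.80 × 0.15 = 12.0 points. In whole eyes, if 8 of 153 are dropped, 102/145 = 70.3% becomes 102/153 = 66.7%.

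**Effect on the between-arm difference (OMNI minus comparator).**

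| Available-data rates | k, OMNI / comparator | Available-data difference | Failures counted |
|---|---|---|---|
| 70% / 70% | 5% / 5% | 0 | 66.5 − 66.5 = 0 |
| 70% / 70% | 5% / 15% | 0 | 66.5 − 59.5 = +7.0 |
| 70% / 70% | 15% / 5% | 0 | 59.5 − 66.5 = −7.0 |
| 75% / 65% | 5% / 5% | +10.0 | 71.25 − 61.75 = +9.5 |

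The sign of the change depends on which arm loses more eyes. With equal losses the change is small.

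**The case against.** The strongest reply is that 10.4.4 never says secondary-procedure eyes are excluded. A binary endpoint can record a failure without a pressure reading, and the 8.10 failure rule is not limited to the primary endpoint, so the two sections could be read together with these eyes as non-responders. That reading is possible, and the text is better called unreconciled than openly contradictory. But 10.4.4 names a different data rule, and 10.4.3 shows how the plan words things when the primary rule is meant to carry over. An analyst following 10.4.4 alone would drop these eyes.

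A second reply is that failures are visible elsewhere: in the primary analysis, in the safety endpoint on secondary interventions, and in 10.4.5, which plans time-to-intervention analyses with log-rank tests and DIOP bands stratified by medication use or secondary surgery. This stands and limits the harm. It does not correct the responder rates themselves.

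Some stronger readings do not hold:

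- **That failed washout also contradicts 8.10.** Section 8.10 covers only secondary IOP-lowering interventions. For failed washout the inconsistency is with 10.4.1, and an exploratory endpoint may follow a different rule if that is stated and intended.
- **That the between-arm comparison is biased in a known direction.** The documents contain nothing from which to derive this.
- **That a 12-month DIOP below 6 mmHg should fail the 20% endpoint to match the primary.** The criterion in 10.4.1 is an IOP below 6 at month 1 or later, not specifically the 12-month DIOP, so the two rules would not match.
- **That the medication-count endpoint ("Mean change in the number of ocular hypotensive medications compared to Screening") needs the last count carried forward.** Nothing in the documents supports that choice, and 10.4.5 deliberately leaves eyes with secondary surgery out of its by-visit counts.

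**Conclusion.** The point holds for the two responder endpoints. For secondary-procedure eyes, 10.4.4 read literally conflicts with 8.10 in two ways: most lose their place in the denominator, and a late-treated eye may count as a success. Eyes that cannot safely be washed out are handled inconsistently with the primary analysis. Relative to counting these eyes as failures, the planned rule can only raise an arm's responder rate or leave it unchanged.

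The inflation is rate × k, plus any late-treated eyes counted as responders. The range of 1.0 to 12.0 points rests entirely on assumed rates and should not be read as a forecast. The primary inference is unaffected. The correction is still worth making before results are known, because both endpoints are listed in 6.1 and receive between-arm estimates with confidence intervals.

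**What to change.** Amend 10.4.4 as follows:

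1. Score every AT eye with a secondary IOP-lowering intervention before the 12-month washout as a non-responder on both endpoints, whether or not a 12-month DIOP was observed, as 8.10 requires.
2. Score eyes that could not be washed out at month 12 for safety reasons the same way, in line with 10.4.1.
3. State the denominator, and say that both groups are in it.
4. Keep the available-data rates as a supplementary display, labelled as such.

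The cost is a few sentences in the plan and a changed denominator, using data already collected. The downside is that the reported responder rates will be somewhat lower.

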10.4.5 ADDITIONAL EFFECTIVENESS ANALYSES

The analyses described in this section are exploratory in nature. All the analyses will be based on the observed data of the AT population by the three study groups.

- Count and percent of subjects with the following DIOP change from baseline to 12 months stratified by the use of ocular hypotensive medication and/or SSI that can affect the IOP:
 - 40% ≤ Change (i.e. increase ≥ 40%)
 - 30% ≤ Change < 40% (i.e. 30% ≤ increase < 40%)
 - 20% ≤ Change < 30% (i.e. 20% ≤ increase < 30%)
 - 10% ≤ Change < 20% (i.e. 10% ≤ increase < 20%)
 - 0% < Change < 10% (i.e. 0% < increase < 10%)
 - Change = 0% (i.e. no change)
 - 10% < Change < 0% (i.e. 0% < decrease < 10%)
 - 20% < Change ≤ -10% (i.e. 10% ≤ decrease < 20%)
 - 30% < Change ≤ -20% (i.e. 20% ≤ decrease < 30%)
 - 40% < Change ≤ -30% (i.e. 30% ≤ decrease < 40%)
 - 50% < Change ≤ -40% (i.e. 40% ≤ decrease < 50%)
 - Change ≤ -50% (i.e. decrease ≥ 50%)
- Count and percent of subjects with the following DIOP 12 months stratified by the use of ocular hypotensive medication and/or SSI that can affect the IOP:
 - ≥6 mmHg to ≤ 21 mmHg
 - ≥6 mmHg to ≤ 18 mmHg
 - ≥6 mmHg to ≤ 15 mmHg
 - ≥6 mmHg to ≤ 12 mmHg
- IOP, IOP change, and IOP percent change from baseline at each visit (excluding use of ocular hypotensive medication and/or SSIs that can affect the IOP)
- The number of ocular hypotensive medications and change in the number of ocular hypotensive medications from screening to each post-operative

examination (including at 12 months prior to washout) excluding subjects treated with SSIs that can affect the IOP.

- The survival analysis (Kaplan Meier curve) with the log-rank test for the time to the first secondary surgery intervention (SSI) for controlling the IOP.
- The survival analysis with the log-rank test for the time to the first ocular hypotensive medications at or after 1 month postoperative. The analysis will include the cases with medications taken before 1 month and ongoing after 1 month.
- The survival analysis with the log-rank test for the time to the first SSI or the first ocular hypotensive medications at or after 1 month postoperative, whichever comes first.

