8.7 SURGICAL PROCEDURE

Only eyes with uneventful cataract extraction will receive one of the following surgical procedures based on randomization:

1. Ab-interno transluminal viscoelastic delivery (up to 360 degrees) and trabeculotomy (at least 180 degrees and up to 360 degrees) using the OMNI Surgical System
2. Ab-interno transluminal viscoelastic delivery (up to 360 degrees) using the OMNI Surgical System
3. [REDACTED]

Eyes with complications related to previous glaucoma interventions or cataract extraction (such as posterior capsular rent or vitreous presentation) should be exited from the study. The region where the trabeculotomy procedure is performed (e.g. superior hemisphere) and the extent of trabeculotomy should be recorded on the case report forms.

[REDACTED]

[REDACTED]

Surgeons should follow their standard intra-operative and peri-operative medication regimen.

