8.10 MANAGEMENT OF IOP AFTER SURGERY

In general, the primary consideration for the reintroduction of hypotensive medication is the preservation of the retinal nerve fiber layer, optic nerve and visual field.

[REDACTED] Administration of glaucoma medication in subjects with IOP < 21 mmHg will be considered on a case-by-case basis by the study Investigator and the sponsor.

No more than one ocular hypotensive agent should be added at a single visit or within a 2-week period, without prior approval of the sponsor.

In the event of a steroid response increase in IOP due to prolonged anti-inflammatory regimen, the guidelines above to treat increase in IOP should be followed; however, topical hypotensive medications should be discontinued once the topical steroid has been discontinued.

Since the study population is undergoing angle surgery involving use of an ophthalmic viscoelastic agent, which is known to cause IOP spikes in some patients in the immediate postoperative period, use of glaucoma medications in the first month after surgery will be allowed at the discretion of the study Investigator. This short-term use of glaucoma medications in the immediate postoperative period will not be considered "rescue therapy" and will not be considered in the effectiveness analyses for the study.

For subject safety, a change in medical therapy may be implemented or additional surgical measures may be performed at any time during the study at the Investigator's discretion in the event it is required. The primary concern of the Investigator and

Sponsor at all times is the health and safety of the subjects. Usage of hypotensive medications specifically indicated for prevention of IOP spikes following Nd:YAG capsulotomy and administered for up to 72 hours after Nd:YAG capsulotomy will not be considered rescue therapy.

Medications which have been re-started by the Investigator may be discontinued if the Investigator's judgment is that the target intraocular pressure has been reached and the continued use of some or all of the therapy may not be required. Discontinuation of medications after re-introduction is recommended to be in the reverse order of re-introduction. The rationale for discontinuation should also be documented in the subject's medical record.

A record of all ocular hypotensive medications added, discontinued or changed will be documented on the appropriate CRF for each scheduled visit or on a CRF for an Unscheduled Visit, if necessary.

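### The two exploratory medication survival analyses in 10.4.5 do not carry over the 8.10 exception for short Nd:YAG prophylaxis, so as written it counts as an event

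*Combined protocol and SAP*

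**What the plan says.** Section 10.4.5 is declared exploratory and uses observed data from the As Treated population by the three study groups. Two of its three survival bullets involve medication. One analyses "the time to the first ocular hypotensive medications at or after 1 month postoperative"; the other analyses "the time to the first SSI or the first ocular hypotensive medications at or after 1 month postoperative, whichever comes first". Neither limits the event by indication or duration. The only further counting rule, attached to the first of the two, widens the event: "The analysis will include the cases with medications taken before 1 month and ongoing after 1 month".

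Section 8.10 names two uses of pressure-lowering drugs that are not rescue therapy. The first is discretionary use in the first month, which in addition "will not be considered in the effectiveness analyses for the study". The second is use to prevent pressure spikes after laser capsulotomy: drugs "administered for up to 72 hours after Nd:YAG capsulotomy will not be considered rescue therapy". The same section requires full recording: "A record of all ocular hypotensive medications added, discontinued or changed will be documented on the appropriate CRF".

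Section 8.7 makes cataract extraction common to all arms: "Only eyes with uneventful cataract extraction will receive one of the following surgical procedures based on randomization".

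**The concern.** The 1-month cut-off in 10.4.5 deals with the first exception in 8.10. Nothing there deals with the second. Since 8.10 sends every pressure-lowering drug to a CRF, Nd:YAG prophylaxis should be in the analysis data. A programmer following 10.4.5 would date the event at the capsulotomy. Only the first event counts, so a later restart of medication because pressure is uncontrolled would not be seen.

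Capsulotomies are foreseeable: every treated eye has had cataract extraction, posterior capsule opacification is graded at the slit lamp (Appendix A, 19.7), and 8.10 contains a rule for the laser. At stake is what the two curves mean. They would mix need for pressure control with a short precaution that the protocol itself sets apart from rescue. The bullet on time to first SSI alone is not affected.

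**Working it through.** **1. Texts side by side.**

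| Use of pressure-lowering drugs | 8.10 | Event in 10.4.5? |
|---|---|---|
| First month, short term | Not rescue; left out of effectiveness analyses | No, through the cut-off |
| Started in first month, ongoing after it | Not addressed in the visible text | Yes, stated |
| Up to 72 hours after Nd:YAG, after month 1 | Not rescue; silent on effectiveness analyses | Yes, by the literal wording |

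**2. The plan's own figure.** The documents give no event count, effect size or power for these curves. The only related figure is enrolment: 411 completers / 3 = 137 per arm; 137 / 0.9 = 152.2, rounded up to 153; 153 × 3 = 459, as stated. I use 153 per arm below.

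**3. Model.** Take constant, independent hazards: h for true medication need and y for Nd:YAG prophylaxis, each equal to −ln(1 − risk) over the horizon.

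- Observed hazard ratio = (h_OMNI + y_OMNI) / (h_control + y_control).
- Observed medication-free survival = true survival × (1 − Nd:YAG risk).
- Approximate power of a two-group log-rank test with d events, two-sided 0.05 = Φ(½·√d·|ln HR| − 1.96).

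**4. Equal Nd:YAG use.** Assumptions, none from the documents: 12-month horizon, control medication risk 30%, true hazard ratio 0.60, no dropout. Then h_control = −ln 0.70 = 0.357 and h_OMNI = 0.6 × 0.357 = 0.214. At 10% Nd:YAG use y = −ln 0.90 = 0.105, so the observed ratio is (0.214 + 0.105) / (0.357 + 0.105) = 0.69.

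| Nd:YAG use, each arm | Medication-free, control | Medication-free, OMNI | Hazard ratio | Events | Power |
|---|---|---|---|---|---|
| 0% (not counted) | 70.0% | 80.7% | 0.60 | 75 | 60% |
| 5% | 66.5% | 76.7% | 0.65 | 87 | 52% |
| 10% | 63.0% | 72.7% | 0.69 | 98 | 45% |
| 20% | 56.0% | 64.6% | 0.75 | 122 | 34% |
| 30% | 49.0% | 56.5% | 0.80 | 145 | 27% |

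A log-rank simulation (4,000 runs per setting) agrees: power falls from about 59% to 45% at 10% Nd:YAG use, and from about 60% to 35% at 20%.

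**5. Range.** For control risks of 20–50%, true ratios of 0.5–0.7 and equal Nd:YAG use of 5–30%, the ratio moved toward 1 in every case. The smallest shift was 0.70 to 0.72 (control 50%, Nd:YAG 5%); the largest was 0.50 to 0.81 (control 20%, Nd:YAG 30%).

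**6. Longer horizon.** With assumed 36-month risks of 40% and 25%, h = 0.511 and 0.288, and the true ratio is 0.56. Equal Nd:YAG use of 10%, 20% and 30% gives 0.393/0.616 = 0.64, 0.511/0.734 = 0.70 and 0.644/0.867 = 0.74.

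**7. Unequal use** (control medication risk 30%, 12 months).

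| True hazard ratio | Nd:YAG, control / OMNI | Observed ratio |
|---|---|---|
| 0.60 | 20% / 10% | 0.55 |
| 0.60 | 10% / 20% | 0.95 |
| 1.00 | 20% / 20% | 1.00 |
| 1.00 | 20% / 10% | 0.80 |
| 1.00 | 10% / 20% | 1.25 |

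The observed ratio is a weighted average of the true ratio and the Nd:YAG ratio. With no true difference and equal use, the simulated type I error stayed at 5%.

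**The case against.** The strongest reply is that this is exploratory and small. Neither the primary endpoint nor the sample size uses these curves. Medication burden is also assessed elsewhere: 10.4.4 compares the change in number of medications to 12 months, and 10.4.5 tabulates medication counts at each visit. A course of at most 72 hours would seldom overlap a visit, so those results hardly depend on this rule. All of that stands and limits the severity.

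A reader might infer that 10.4.5 directly contradicts 8.10. The documents do not support that. The first-month sentence removes those drugs from the effectiveness analyses; the Nd:YAG sentence says only that they are not rescue. Section 10.4.5 speaks of first medication, not of rescue or failure. Part of the medication-reintroduction text in 8.10 is also blacked out. What remains is a gap between two sections that two analysts could fill differently.

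A reader might also infer that the rule always pulls the comparison toward no difference. That needs a true difference and similar Nd:YAG use. Similar use is plausible, because all arms have cataract extraction and allocation is random, but it is not stated.

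Finally, a reader might infer that a planned hazard ratio, pairwise contrast or 36-month result loses power. Section 10.4.5 names only a log-rank test, with no effect estimate, pairwise comparison, power target or horizon for these curves. The ratios and power figures above are my way of showing dilution.

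**Conclusion.** The point holds as a minor one. Under the literal event definition, a short prophylactic course after Nd:YAG capsulotomy is an event in both medication survival analyses and masks later true rescue in that eye. Understated medication-free survival follows in any arm where such courses occur, whether or not the arms differ. The effect on the comparison is conditional: dilution with a true difference and similar use, possible false difference with unequal use, and no bias with no difference and equal use.

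The size cannot be fixed from the documents. Under the 12-month assumptions shown, equal use of 5–20% would move a hazard ratio of 0.60 to 0.65–0.75. These figures rest on assumed rates, constant independent hazards, no dropout, and recorded prophylaxis in that share of eyes. The primary analysis and the 459 enrolment figure are unaffected.

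**What to change.** In both medication bullets of 10.4.5, define the event as the first ocular hypotensive medication at or after 1 month, other than Nd:YAG use that 8.10 states is not rescue therapy. Naming the Nd:YAG use keeps the clause from colliding with the existing sentence on early drugs that continue past 1 month, which can stay. Report the all-medication definition as a sensitivity analysis, so that a reader can see whether the choice matters.

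Record indication with start and stop dates on the medication CRF. Section 8.10 requires that additions, discontinuations and changes be recorded, but the documents do not say that indication is captured.

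The cost is one clause, one added CRF field and a small classification judgement, which the all-medication definition avoids. The classification should be made without knowledge of treatment group where possible. Nothing changes in how eyes are treated.
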